## LIST OF ABBREVIATIONS AND RELEVANT DEFINITIONS

|                |  |
|----------------|--|
| ABR     | General Assessment and Registration form (ABR form), the application form that is required for submission to the accredited Ethics Committee; in Dutch: Algemeen Beoordelings- en Registratieformulier (ABR-formulier) |
| AE      | Adverse Event   |
| AR      | Adverse Reaction  |
| CA      | Competent Authority   |
| CCMO    | Central Committee on Research Involving Human Subjects; in Dutch: Centrale Commissie Mensgebonden Onderzoek  |
| CECS    | Chronic Exertional Compartment Syndrome   |
| CV      | Curriculum Vitae  |
| DSMB    | Data Safety Monitoring Board  |
| EU      | European Union  |
| EudraCT | European drug regulatory affairs Clinical Trials  |
| GCP     | Good Clinical Practice  |
| GDPR    | General Data Protection Regulation; in Dutch: Algemene Verordening Gegevensbescherming (AVG)   |
| IB      | Investigator's Brochure   |
| IC      | Informed Consent  |
| ICC     | Intraclass Correlation Coefficient  |
| ICPM    | Intra-Compartmental Pressure Measurement  |
| IMP     | Investigational Medicinal Product   |
| IMPD    | Investigational Medicinal Product Dossier   |
| METC    | Medical research ethics committee (MREC); in Dutch: medisch-ethische toetsingscommissie (METC)   |
| NIAPS   | Netwerk Inspannings Afhankelijke PijnSyndromen; Dutch Network of hospitals that treat patients with CECS and developed a CECS-specific questionnaire including symptoms and function  |
| (S)AE   | (Serious) Adverse Event   |
| SPC     | Summary of Product Characteristics; in Dutch: officiële productinformatie IB1-tekst  |
| Sponsor | The sponsor is the party that commissions the organisation or performance of the research, for example a pharmaceutical   |

company, academic hospital, scientific organisation or investigator. A party that provides funding for a study but does not commission it is not regarded as the sponsor, but referred to as a subsidising party.

|              |   |
|--------------|---|
| SUSAR | Suspected Unexpected Serious Adverse Reaction  |
| UAVG  | Dutch Act on Implementation of the General Data Protection Regulation; in Dutch: Uitvoeringswet AVG        |
| WMO   | Medical Research Involving Human Subjects Act; in Dutch: Wet Medisch-wetenschappelijk Onderzoek met Mensen |

## SUMMARY

### Rationale:

Chronic Exertional Compartment Syndrome (CECS) is one of the exercise-induced lower leg pathologies. Recognition by patients and physicians is not optimal. As a consequence, many patients are undiagnosed and are forced to stop their sporting activities. To diagnose CECS, a doctor should be alerted by a patient's history and a physical examination. If both suggestive of CECS, an invasive intra compartmental pressure measurement (ICPM) in the affected compartment may be performed. During the ICPM a catheter is placed into the muscle via a hollow needle. The ICPM is not flawless in terms of accuracy and reproducibility and has a low intra-observer reproducibility. Moreover, haematoma or other tissue damage may occur following an ICPM. Nevertheless, this *invasive* ICPM is in 2022 still considered the 'gold-standard' diagnostic tool for CECS, in the absence of a better one.

A novel non-invasive tool for CECS is possibly provided by measuring muscle tissue compressibility. The idea is, that muscle tissue with a high pressure (as in CECS patients) requires more external force to compress, compared to tissue with a low pressure. The study device used in this study, the CPM#1 device, is based on this principle. The CPM#1 device is non-invasive, not painful, very user friendly, and the measurement can be executed as an 'office procedure' in a couple of minutes. This study will focus on determining the reliability of the device in healthy volunteers.

### Objective:

The primary objective is

- To validate the *inter*-observer reliability of compressibility measurements with the CPM#1 device during rest in healthy volunteers.

Secondary objectives are

- To validate the *intra*-observer reliability of compressibility measurements with the CPM#1 device during rest in healthy volunteers.
- To investigate the effect of exercise on compressibility immediately, one minute, and five minutes after exercise in healthy volunteers.
- To map the invasiveness of the compressibility measurement with the CPM#1 device.

### Study design:

This study is a performance validation pilot with the CPM#1 device that is tested in healthy volunteers. There will only be one study arm, no comparator, and no randomization.

**Study population:**

35 healthy subjects without signs or symptoms of CECS.

**Intervention (if applicable):**

Participants will be measured with the CPM#1 device in rest and after a treadmill exercise.

**Main study parameters/endpoints:**

Inter-observer reliability of the compressibility measured with CPM#1 device.

**Nature and extent of the burden and risks associated with participation, benefit and group relatedness:**

Healthy subjects will undergo several compressibility measurements, both before and after a treadmill exercise. They will also complete a NIAPS (Netwerk Inspannings Afhankelijke PijnSyndromen) questionnaire and an 'experience' questionnaire. The harm associated with the CPM#1 device is none. However, the subjects will not benefit from this study.

## 1. INTRODUCTION AND RATIONALE

Chronic Exertional Compartment Syndrome (CECS) is one of the exercise-induced lower leg pathologies. The prevalence among a general population may be up to 10%. Nevertheless, recognition of CECS by patients and physicians is not optimal. This, on average, causes a delay of 30 months before visiting a surgeon. As a consequence, many patients are unknowingly and undiagnosed forced to stop their sporting activities. As many are military or semi-professional sportsmen, CECS may have a tremendous impact on daily life and career. A subgroup of CECS patients will benefit from a surgical intervention (namely fasciotomy). Recent data suggest that outcome and diagnostic delay are related.

Pathophysiology and biomechanics of CECS are not fully understood. However, it is generally accepted that CECS is caused by an unusual pressure build-up within a muscle compartment during exertion. This inadequate pressurizing results in diminished vascularisation of the fascia or possibly stretch on the fascia, which consequently results in pressure or traction on nerves and blood vessels causing pain, tightness, cramps, strength loss, or occasionally numbness. Symptoms may occur in four different compartments, namely the anterior-, lateral-, deep posterior- and superficial posterior compartment. The anterior compartment CECS patients (ant-CECS) is mostly affected (40-60%).

To diagnose CECS, a doctor should be alerted by both patient's history (pain, tightness in lower leg muscle) and a physical examination (tender muscle palpation after exercise). If suggestive of CECS, an invasive muscle tissue pressure measurement (intra compartmental pressure measurement, ICPM) of the symptomatic compartment may be advised. This is particularly true as non-invasive treatments for possible CECS were up till then ineffective and a surgical procedure is considered. During this procedure, a catheter is placed into a muscle via a hollow needle using local anaesthesia. The Pedowitz criteria are used for diagnosing CECS. By these criteria, a patient is suffering from CECS if an ICPM in the affected compartment is >15 mmHg during rest, or > 30 mmHg one minute after a provocative exercise, or >20 mmHg after five minutes.

However, an ICPM is occasionally quite a painful procedure. In addition, there is a small chance of haematoma, infection or nerve damage. Moreover, an ICPM is not flawless in terms of accuracy and a low intra-observer reproducibility was found. Large et al showed that, on cadaveric limbs, just 31% of the physicians performing an ICPM used the correct technique. Interestingly, only 60% of these correct measurements were within the five mmHg range of the standard pressure. Vogels et al showed that, of all available ICPM equipment, only the Stryker device and arterial line accurately measured ICPM in a porcine gluteal muscle sample.

Considering these suboptimal test characteristics in non-human models, one could argue that measuring patients will introduce even more variance, especially when, apart from rest measurements, also exercise measurements are involved. Despite these drawbacks, in 2022 an *invasive* ICPM is still considered the 'gold-standard' diagnostic tool for CECS, in the absence of a better one.

Over the years, a number of efforts have focused on identifying a reliable *non-invasive* diagnostic technique for CECS. A novel tool is possibly provided by measuring tissue compressibility. The idea is that muscle tissue with a high pressure requires more external force to compress to a certain degree compared to tissue with a low pressure. The study device which will be used in this study, the Comprenium Compartmental Compressibility Monitoring System (in short, CPM#1 device), is based on this principle. This hand-held ultrasound-based tool measures the distance between various standard landmarks in the lower leg compartment at 10mmHg and at 80mmHg external pressure. The difference in length reflects the compressibility of the compartment (and thus its pressure). The CPM#1 device is non-invasive, not painful, very user friendly, and the measurements can be executed as an 'office procedure' in a couple of minutes. Bench tests with the CPM#1 have shown a good *inter- and intra-observer* reproducibility. An experienced observer, and even an inexperienced observer, were able to produce an inter-observer reliability of 0.945 when applying the same protocol on separate days (Máxima Medical Center, unpublished data). Anwader et al. showed an intra-observer reliability of 0.89 for an experienced and 0.79 for an inexperienced observer with an inter-observer reliability of 0.78.

The present study will focus on determining reliability of the device and its usage in healthy volunteers. At a later stage, it is intended that patients suggestive of having CECS will also undergo these measurements.

## 2. OBJECTIVES

Primary objective is to validate the *inter-observer* reliability of compressibility measurements with the CPM#1 device during rest.

The secondary objectives are:

- To validate the *intra-observer* reliability of compressibility measurements with the CPM#1 device during rest in healthy volunteers.
- To investigate the effect of exercise on compressibility immediately, one minute, and five minutes after exercise in healthy volunteers.
- To map the invasiveness of the compressibility measurement with the CPM#1 device.

We estimate that for the primary objective and first secondary objective the ICC will be  $\geq 0.75$  and for the second secondary objective that there will be a difference  $<2\%$  between compressibility before and after exercise.

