#### 4.4 Sample size calculation

As data on this device are scarce, a pragmatic sample size rationale is pursued based on previous studies that were made available to us by the company. Moreover, this study is not aimed at hypothesis testing, rather, we aim to estimate the ICC with certain precision. With the predecessor of CPM#1 it has been shown that an  $ICC \geq 0.75$  is achievable and thus demonstrated a good inter-observer reliability.

[figure not shown]
Measuring the left and right m. tibialis anterior in two directions, an expected  $ICC = 0.8$  (based on bench tests) and a one-sided 95% target confidence interval width of 0.05 based on three observers, a sample size of 140 is required. Since we measure 4 'samples' per participant (each leg the m.tibialis anterior at two different approaches, see section 5.1), we aim to include 35 healthy volunteers (140:4). We do not include dropouts in our calculation since we perform only one 90 minute session without follow-up. Participants who do not complete the

measurements will be replaced for new inclusions, such that we will have a complete data set of 35 participants in the end.

To power for the measurement directly after exercise, using dependent sample T-test with an expected effect size of 0.4 (based on results from bench test), an  $\alpha$  of 0.05 and power ( $\beta-1$ ) of 0.9, we would require 68 samples. Since the strict timing of the measurements after exercise only allows the measurement of one sample (one compartment using one approach), all participants will undergo two exercise sessions ( $2 \times 35 = 70$ ).

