#### 8.1.2 Secondary study parameters/endpoints (if applicable)

Intra-observer variance of compressibility within three observers using intra-class correlation coefficients (two-way random effects, single observer, absolute agreement).

Immediate, one minute, and five minutes post-exercise compressibility compared to the observer's rest measurement compressibility.

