### 8.2 Randomisation, blinding and treatment allocation

Randomisation:

The order of the measurements within a subject will not be completely randomised. However, we will randomize the order of the observers preventing bias due to fixed order of measurement. Also we will randomize the site of measurement where the observer will start (thus left or right leg) and approach (notch or interosseous membrane), by means of an online block randomization tool.

Blinding:

Observers will not be blinded to the results (i.e. the compressibility displayed in percentage), as distances cannot be made invisible during determining distances. However, after determining the distances, the device will calculate the CP value itself. Therefore this CP value is not influenced directly by the observer.

Observers will be instructed to not search for the previous measurements performed by previous observers. They are also instructed to not communicate the measurement results among each other.

Treatment allocation:

N.A.

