## 10. STATISTICAL ANALYSIS

Intra-class correlation coefficients will be calculated as indicated below and described using 95% confidence intervals.

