### 10.2 Secondary study parameter(s)

The secondary endpoint of intra-observer variability will be the intraclass correlation coefficient (ICC) of agreement within three observers, four sites per subject, and four repetitions per measurement. The ICC will be assessed using a two-way random effects model. Both subjects and repetitions will be included as random effects. The repeated measures will be analysed for each observer separately and this agreement serves to address differences between observers. “Good reliability” classification will be reached if the lower bound of the computed ICC confidence interval does not fall below 0.75

The second secondary endpoint is the comparison between post-exercise (immediate, one minute, and five minutes) compressibility and rest compressibility. This will be analysed using a dependent sample t-test.

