### 10.3 Other study parameters

Additional secondary analyses (exploratory analyses) of outcomes not foreseen in this protocol may be undertaken to explore additional features of the performance, acceptability and safety of the CPM#1 device. Where possible these will be specified in the pre-defined statistical analysis plan.

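### The planned t-test of zero difference cannot show whether the expected exercise difference below 2% holds, no interval is planned for it, and the 2% has no stated scale

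*Combined protocol and SAP*

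**What the plan says.** The second of the secondary objectives is to study what exercise does to compressibility immediately, at one minute and at five minutes. Section 2 closes with two expectations in one sentence. The ICCs should be at least 0.75, and the authors estimate "for the second secondary objective that there will be a difference" below 2% between the values before and after exercise.

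The two expectations are then treated differently.

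- **ICC.** Section 10 states: "Intra-class correlation coefficients will be calculated as indicated below and described using 95% confidence intervals". Sections 10.1 and 10.2 judge the 0.75 by the lower confidence bound.
- **Exercise difference.** Section 8.1.2 defines the endpoint as "post-exercise compressibility compared to the observer's rest measurement compressibility". Section 10.2 says of the analysis only: "This will be analysed using a dependent sample t-test". It mentions no estimate, interval or rule for the 2%.

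Section 4.4 sizes the exercise comparison "using dependent sample T-test with an expected effect size of 0.4", giving 68 samples. To reach that number, "all participants will undergo two exercise sessions", one per leg, which yields 70. Section 8.2 describes the device output as "the compressibility displayed in percentage".

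**The concern.** A paired t-test asks whether the mean change differs from zero. The expectation in Section 2 asks whether the change is small. A change of 1 point can be significant and still lie below 2%. A non-significant result can come with an interval that reaches beyond 2%. The p-value alone separates neither case.

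The 2% is also open to two readings. If compressibility falls from 20% to 19%, that is 1 percentage point but a 5% relative change. The first is inside 2% and the second is outside it.

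At stake is the interpretation of one secondary objective. The report will be read against its only quantitative expectation, and the planned output does not address that expectation.

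**Working it through.** **Inputs from the protocol.** Expected difference below 2% (Section 2). Effect size 0.4, alpha 0.05, power 0.9, 68 samples required, 2 × 35 = 70 planned (Section 4.4).

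**Assumptions.** The 2% means percentage points. The SD of the paired change is not given, so 3, 4 and 5 points are shown. Steps 1, 3 and 4 treat the 70 legs as independent, as Section 4.4 does.

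**Step 1: reproduce the 68.** Two-sided paired t-test power comes from the non-central t distribution with n − 1 df and non-centrality d√n. With d = 0.4, power is 0.897 at n = 67, 0.902 at n = 68 and 0.910 at n = 70. The 68 is confirmed (a one-sided test would need 55). It is the size for detecting a non-zero change of 0.4 SD, and the 2% does not enter.

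**Step 2: which SDs fit the plan's own figures.** If the 0.4 effect size and the difference below 2% describe the same effect in points, then 0.4 × SD < 2, so SD < 5. Larger SDs are illustrative only.

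**Step 3: how the p-value behaves.** Non-centrality = (true change / SD) × √70, with 69 df.

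| SD (points) | Chance of p < 0.05, true change 1 point | Chance of p > 0.05, true change 2 points |
|---|---|---|
| 3 | 0.79 | 0.0002 |
| 4 | 0.54 | 0.015 |
| 5 | 0.38 | 0.09 |

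**Step 4: two possible results.** SE = SD/√70; 95% CI = change ± 1.995 × SE.

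- SD 3, observed change 1.0: SE = 0.359, t = 2.79, p = 0.007, CI 0.28 to 1.72. Significant, and wholly below 2.
- SD 5, observed change 1.15: SE = 0.598, t = 1.92, p = 0.058, CI −0.04 to 2.34. Not significant, and a change below 2 is not supported. This case sits at the boundary from Step 2.

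**Step 5: two legs per participant.** With legs averaged, the participant SD is SD × √((1 + ρ)/2), where ρ is the assumed between-leg correlation of the change; n = 35, 34 df, t = 2.032.

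- SD 5, ρ = 0.5: participant SD = 5 × √0.75 = 4.33; half-width = 2.032 × 4.33/√35 = 1.49 points. On 70 independent legs it is 1.995 × 5/√70 = 1.19.
- SD 3, observed change 1.0, ρ = 0.9: the averaged analysis gives p = 0.051 and a CI of −0.004 to 2.004, while the leg-level test in Step 4 gives p = 0.007. A leg-level test beside a participant-level interval can therefore disagree.
- Power of the participant-level t-test for the planned 0.4 SD, using d = 0.4/√((1 + ρ)/2) and n = 35: ρ = 0 gives d = 0.566 and power 0.90; ρ = 0.5 gives d = 0.462 and power 0.76; ρ = 0.9 gives d = 0.410 and power 0.66.

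**The case against.** The best defence is that the plan never promises to test 2%. Section 2 presents it as an estimate under a neutral objective. Section 4.4 does not size on it, and a paired t-test is an ordinary analysis of an exercise effect. Where the authors wanted a criterion they wrote one, as they did for the ICC. All of this stands. A reader might infer that 2% is an equivalence margin and that the study is wrongly designed or underpowered for equivalence. The documents do not support that, because no margin or success rule is stated.

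A reader might also infer that a change of 2 points or more is likely to be missed and reported as no effect. At an assumed SD of 8 the chance of non-significance at a true 2 points would be 0.46. But the plan's own 0.4 and 2%, if they describe the same effect in points, imply an SD below 5, where the chance in Step 3 is under 0.09. The SD 8 figure should carry no weight. If 2% is relative, or the 0.4 refers to something else, this bound fails, but so do the point-scale figures.

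Two textual defences are weaker. Section 4.4 says that the study's aim is estimation, but that sentence concerns ICC precision and the same section then powers a t-test. Section 10.3 says of additional exploratory analyses: "Where possible these will be specified in the pre-defined statistical analysis plan". No such separate plan was supplied, so the fair statement is that nothing supplied fills the gap. Likewise, Section 10 is silent on an interval for the change and does not rule one out. Software usually prints one, but the plan does not commit to reporting it or comparing it with 2%.

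**Conclusion.** The point holds as a minor but cheap improvement. The planned p-value cannot confirm or refute a difference below 2%, no interval for the change is planned, and the scale of the 2% is undefined.

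On the SDs compatible with the plan's figures, the main risk is that a significant result is taken to contradict the expectation: 79% of trials at SD 3 and 54% at SD 4 when the true change is 1 point. The opposite error is much less likely on 70 independent legs. These sizes rest on an assumed SD, the percentage-point reading and independent legs, so the practical size in this study is unknown. The mismatch between test and expectation does not depend on those assumptions.

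The primary inter-observer ICC analysis is not affected, and the paired t-test is not wrong for asking whether there is any change.

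**What to change.** **Section 10.2.** Add text to this effect:

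- At each of the three time points, report the mean change (post-exercise minus the same observer's rest value for the same leg and landmark) with a 95% CI.
- Base the CI and the paired comparison on the same participant-level unit, for example legs averaged (n = 35) or a mixed model with a participant random effect, so that they cannot disagree.
- Regard a difference below 2% as supported at a time point only if the whole 95% CI lies within −2% to +2%. Do not take a non-significant p-value as support.

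**Section 2.** State whether 2% is percentage points of the compressibility value or relative change from rest. Alternatively, delete the 2% expectation; the interval is still worth reporting.

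**Cost.** A few sentences, with the same data and the same number of participants. There are two downsides.

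- The participant-level interval is wider and may be too wide to support a difference below 2%. At SD 5 and ρ = 0.5 the half-width is about 1.49 points, against 1.19 on 70 independent legs. With zero true change, the chance that the CI lies within ±2 points is then 0.51 (0.80 at ρ = 0, 0.31 at ρ = 0.9; 400,000 simulated trials).
- The nominal 90% power of the t-test is not kept if the legs are correlated (0.76 at ρ = 0.5, Step 5). Section 4.4 should say so.
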